9.2 SETTING

This retrospective database study will leverage the GE EMR data from October 1, 2013 to April 30, 2018. The EMR consists of patient data from ambulatory care records in the US and is representative of the US population receiving healthcare in the ambulatory setting. Patients will be included in one of three study cohorts based on prescription history from October 1, 2014 to April 30, 2018, allowing for a 12-month pre-index period to describe patient demographic, clinical and treatment characteristics.

Index date

The index date for the nintedanib (or pirfenidone) cohort will be the date of the first nintedanib (or pirfenidone) prescription during the selection window (from October 1, 2014 to April 30, 2018). The index date for the untreated cohort will be the date of the earliest IPF diagnosis or a randomly assigned date between October 1, 2013 and April 30, 2018.

Pre-index period

[figure not shown]
The pre-index period for each cohort will be the 12 months prior to the index date. Patients will be required to have ≥ 1 diagnosis of IPF during the pre-index period (see additional inclusion criteria described below).

Post-index period

The post-index period for each cohort will start from the index date. Since the study aims to evaluate patient characteristics during the pre-index period, no minimum follow-up will be required for post-index period and no study measures will be assess during the post-index period.

Patient selection is illustrated in Figure 1.

Figure 1. Patient Selection

Nintedanib cohort

Inclusion criteria:

- With ≥ 1 diagnosis for IPF (the International Classification of Diseases, Ninth Revision, Clinical Modification [ICD-9-CM] codes 516.3, 516.31, 515,¹¹ or ICD-10-CM codes J84.112) in the EMR between October 1, 2013 to April 30, 2018
- With ≥ 1 prescription for nintedanib between October 1, 2014 and April 30, 2018 (the selection window)
 - The date of the first prescription will be defined as the index date
- With ≥ 1 record in the EMR database during the 12 months prior to the index date (the pre-index period)
- With ≥ 1 diagnosis of IPF during the 12 months prior to the index date
- Age ≥ 40 on the index date
- will explore also requiring ≥ 1 chest CT scan before first IPF diagnosis during the pre-index period¹²

Exclusion criteria:

- With ≥ 1 diagnosis of other known causes of interstitial lung disease (ILD) on the date of or after the first IPF diagnosis during the pre-index period^{12,13}

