- Other known causes of ILD include conditions such as systemic sclerosis, rheumatoid arthritis, systemic lupus erythematosus, dermatomyositis, polymyositis, Sjögren disease, and hypersensitivity pneumonitis (ICD-9-CM codes 135, 237.7, 272.7, 277.3, 277.8, 446.21, 446.4, 495, 500–505, 506.4, 508.1, 508.8, 516.0, 516.1, 516.32–516.37, 516.2, 516.8, 516.9, 517.0, 517.2, 517.8, 518.3, 555, 710.0, 710.0–710.4, 714.0, 714.81, 720, and 759.5, or ICD-10-CM equivalent codes)^{12,13}
- With ≥ 1 prescription for nintedanib prior to the index date
- With ≥ 1 prescription for pirfenidone prior to or on the index date

Pirfenidone cohort

Inclusion criteria:

- With ≥ 1 diagnosis for IPF (ICD-9-CM codes 516.3, 516.31, 515,¹¹ or ICD-10-CM codes J84.112) in the EMR between October 1, 2013 to April 30, 2018
- With ≥ 1 prescription for pirfenidone between October 1, 2014 and April 30, 2018 (the selection window)
 - The date of the first prescription will be defined as the index date
- With ≥ 1 record in the EMR database during the 12 months prior to the index date
- With ≥ 1 diagnosis of IPF during the 12 months prior to the index date
- Age ≥ 40 on the index date
- will explore also requiring ≥ 1 chest CT scan before first IPF diagnosis during the pre-index period¹²

Exclusion criteria:

- With ≥ 1 diagnosis of other known causes of interstitial lung disease (ILD) on the date of or after the first IPF diagnosis during the pre-index period^{12,13}
 - Other known causes of ILD include conditions such as systemic sclerosis, rheumatoid arthritis, systemic lupus erythematosus, dermatomyositis, polymyositis, Sjögren disease, and hypersensitivity pneumonitis (ICD-9-CM codes 135, 237.7, 272.7, 277.3, 277.8, 446.21, 446.4, 495, 500–505, 506.4, 508.1, 508.8, 516.0, 516.1, 516.32–516.37, 516.2, 516.8, 516.9, 517.0, 517.2, 517.8, 518.3, 555, 710.0, 710.0–710.4, 714.0, 714.81, 720, and 759.5, or ICD-10-CM equivalent codes)^{12,13}
- ≥ 1 prescription for pirfenidone prior to the index date
- ≥ 1 prescription for nintedanib prior to or on the index date

Untreated cohort

Inclusion criteria:

- With ≥ 1 diagnosis for IPF (ICD-9-CM codes 516.3, 516.31, 515,¹¹ or ICD-10-CM codes J84.112) in the EMR between October 1, 2013 to April 30, 2018
 - Index date will be defined as the date of the earliest IPF diagnosis or a randomly assigned date based on the exploratory analyses to be performed on the two treatment cohorts (exploring time from IPF diagnosis to treatment initiation)

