 - will explore requiring ≥ 2 diagnoses for IPF that are ≥ 30 days apart to improve the identification of IPF patients^{12,13}
- With ≥ 1 record in the EMR database during the 12 months prior to the index date (the pre-index period)

- Age ≥ 40 on the index date
- will explore also requiring ≥ 1 chest CT scan before first IPF diagnosis during the pre-index period¹²

Exclusion criteria:

- With ≥ 1 diagnosis of other known causes of interstitial lung disease (ILD) on the date of or after the first IPF diagnosis during the pre-index period
 - Other known causes of ILD include conditions such as systemic sclerosis, rheumatoid arthritis, systemic lupus erythematosus, dermatomyositis, polymyositis, Sjögren disease, and hypersensitivity pneumonitis (ICD-9-CM codes 135, 237.7, 272.7, 277.3, 277.8, 446.21, 446.4, 495, 500–505, 506.4, 508.1, 508.8, 516.0, 516.1, 516.32–516.37, 516.2, 516.8, 516.9, 517.0, 517.2, 517.8, 518.3, 555, 710.0, 710.0–710.4, 714.0, 714.81, 720, and 759.5, or ICD-10-CM equivalent codes)^{12,13}
- With prescription for nintedanib or pirfenidone anytime during the data window

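### If the untreated index date is the earliest IPF diagnosis, the other-ILD exclusion and the one-record rule in Section 9.2 act differently in the treated and untreated cohorts

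*Combined protocol and SAP*

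**What the plan says.** All the rules at issue are in Section 9.2 of the combined protocol and SAP.

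- **Treated index.** "The date of the first prescription will be defined as the index date" for both the nintedanib and the pirfenidone cohort.
- **Untreated index.** The choice is left open. Under Index date: "The index date for the untreated cohort will be the date of the earliest IPF diagnosis or a randomly assigned date between" the first and last days of the data window. In the untreated inclusion list: "Index date will be defined as the date of the earliest IPF diagnosis or a randomly assigned date based on the exploratory analyses" of the treated cohorts, which look at time from diagnosis to treatment.
- **Pre-index period.** "The pre-index period for each cohort will be the 12 months prior to the index date". The next sentence requires at least one IPF diagnosis in that period and is not limited to the treated cohorts.
- **IPF diagnosis criterion.** Both treated lists require at least one "diagnosis of IPF during the 12 months prior to the index date". The untreated list has no such item.
- **One-record rule.** The untreated list requires at least one "record in the EMR database during the 12 months prior to the index date (the pre-index period"). The treated lists have the same requirement.
- **Other-ILD exclusion.** All three cohorts exclude patients with another known cause of ILD coded "on the date of or after the first IPF diagnosis during the pre-index period".

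Section 9.3.3 uses two windows. Covariates are measured over a 12-month baseline that includes the index date, while the treatment-history heading says the pre-index period does not include it.

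**The concern.** Both eligibility rules are tied to the index date, and the index date means different things in different cohorts. For treated patients it is a prescription that follows an IPF diagnosis. For untreated patients it may be the diagnosis itself. The same words can then select different kinds of patient.

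At stake are two of the three primary comparisons in Section 9.3.2.1 (each drug vs untreated) and the treated-vs-untreated propensity model in Section 9.3.2.2. Patients with known-cause ILD would be partly removed from the treated cohorts and kept in the untreated cohort. Patients with little recorded history before their IPF code would be kept among the treated and removed from the untreated. Either could produce a standardized difference that reads as a driver of treatment but comes from the selection rules. Section 9.12 relies on the Section 9.2 identification algorithm to limit misclassification in the untreated cohort, and under this option its other-ILD component would do almost nothing there. Section 9.9 does not list this as a limitation.

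**Working it through.** The plan gives no figure on this point to reproduce. Steps 1 to 3 are logic from Section 9.2. Step 4 is illustration only.

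**Step 1. Other-ILD exclusion.** Count days from index (day 0), with the pre-index period as days −365 to −1.

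- *Untreated, index at earliest IPF diagnosis:* the code must fall on day 0 or later and also on day −1 or earlier. The set is empty. This holds whether the phrase about the pre-index period is attached to the IPF diagnosis or to the other-ILD code. If the index day is counted, one day qualifies (day 0).
- *Treated:* with the first in-window IPF code 30, 90, 180 or 365 days before the prescription, there are 30, 90, 180 or 365 qualifying days.

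**Step 2. One-record rule.**

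- *Treated:* the required IPF diagnosis in days −365 to −1 is itself a record, so the rule removes nobody further.
- *Untreated, index at earliest IPF diagnosis:* the IPF visit is on day 0 and does not count, so a separate record in the preceding 12 months is needed. Without one the patient is removed. If the index day is counted, the IPF visit satisfies the rule and this asymmetry disappears.

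**Step 3. General pre-index diagnosis requirement.** With index at the earliest IPF diagnosis and an index-exclusive window, no untreated patient has a pre-index IPF diagnosis. Read literally for every cohort, the sentence under Pre-index period would empty the untreated cohort.

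**Step 4. Illustrative size.** The documents give no prevalence of other-ILD codes, no delay distribution and no share of patients without earlier records. Every input below is an assumption except the ASD formula for proportions, which is from Section 9.7.1: d = (p₁ − p₂) / √{[p₁(1 − p₁) + p₂(1 − p₂)]/2}.

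*Other-ILD rule.* Suppose a share c of IPF-coded patients receives an other-ILD code within 12 months after the IPF code, at a constant rate λ = −ln(1 − c), and treated search windows are uniform over 0 to 12 months. The share of treated patients removed is R = 1 − c/λ. The share of known-cause ILD left among the treated is (c − R)/(1 − R); among the untreated it stays at c. Take a trait present in 70% of other ILD and 30% of IPF, so its prevalence is 0.30 + 0.40 × the known-cause share.

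| c | λ | R (treated removed) | Left in treated | Trait, treated vs untreated | ASD |
|---|---|---|---|---|---|
| 10% | 0.105 | 5.1% | 5.2% | 0.321 vs 0.340 | 0.041 |
| 20% | 0.223 | 10.4% | 10.7% | 0.343 vs 0.380 | 0.077 |
| 30% | 0.357 | 15.9% | 16.8% | 0.367 vs 0.420 | 0.108 |

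*Record rule.* Suppose a share r of treated patients has no record in the 12 months before the first IPF code and has a comorbidity coded in 30% rather than 60%, with equal true disease. Treated prevalence is 0.6(1 − r) + 0.3r; untreated is 0.6.

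- r = 20%: 0.54 vs 0.60, ASD = 0.06/√[(0.2484 + 0.2400)/2] = 0.121.
- r = 30%: 0.51 vs 0.60, ASD = 0.09/√[(0.2499 + 0.2400)/2] = 0.182.

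**The case against.** **The option has not been chosen.** This is fair and it limits the point. If untreated index dates fall after diagnosis, the exclusion can operate. But the earliest diagnosis is the first option named, and the random-date option as written under Index date does not require the date to follow the diagnosis.

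**The window may include the index day.** Section 9.3.3 does include it for covariates. Applied to eligibility, same-day other-ILD codes would exclude untreated patients and the record-rule asymmetry would go. The wording of Section 9.2 and the treatment-history heading favour the exclusive window, but the plan is not explicit. Even with the index day counted, the other-ILD search covers one day in the untreated cohort against up to 12 months in the treated.

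**The record rule does remove treated patients.** Table 1 in Section 9.5 drops from 2,750 to 2,508 (242 patients) at a record step. That step uses any time before index, and patients with no record before index would also fail the later diagnosis step. It changes where they are counted, not who remains.

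**Other safeguards exist.** Requiring two diagnoses at least 30 days apart, or a prior chest CT, is only to be explored, and neither replaces the other-ILD exclusion.

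**Stronger readings the documents do not support.** A reader might infer that the record rule removes only untreated patients first seen with IPF. It also removes those returning after a gap of more than 12 months and those coded soon after data start on October 1, 2013. A reader might also infer that the 10% threshold is sure to be crossed, since an other-ILD prevalence of about 0.5% against 0% gives an ASD of 0.10. That is the ASD of the other-ILD code itself, which is not a listed covariate, and it supposes complete removal among the treated, where removal is only partial. Finally, visits between diagnosis and prescription can fill in comorbidities for treated patients, which would shrink the record-rule figures.

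**Conclusion.** The concern holds conditionally. With the untreated index at the earliest IPF diagnosis and an index-exclusive pre-index period, the other-ILD exclusion can remove no untreated patient, and the one-record rule binds only in the untreated cohort. That is differential selection in the two treated-vs-untreated primary comparisons and the corresponding propensity model. Nintedanib vs pirfenidone is unaffected, because both cohorts share the same index definition and rules.

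The logic needs no assumption beyond that option and window. The size cannot be derived from the documents. Under the stated assumptions, the other-ILD rule produces ASDs of about 4–11%, with two of three scenarios below the 10% threshold, and the record rule about 12–18%. These show that the effect could matter, not that it will. Separately, the general requirement for a pre-index IPF diagnosis contradicts the earliest-diagnosis option and must be reconciled with it. The point should be settled before the cohorts are built.

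**What to change.** State in Section 9.2 whether the index day belongs to the pre-index period for eligibility, then choose one route.

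1. **Index after diagnosis.** Assign untreated index dates after the first IPF diagnosis, drawn from the diagnosis-to-treatment delay distribution of the treated cohorts, and put the pre-index IPF diagnosis criterion in the untreated list. The existing rules then act alike and the general requirement can be met.
2. **Index at earliest diagnosis.** Define the other-ILD window relative to the first IPF code, identical in all three cohorts and including the date of that code. Apply the prior-record requirement before the first IPF code to all cohorts or to none. Limit the general pre-index diagnosis sentence to the treated cohorts or reword it.

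Under either route, report the number each rule removes, by cohort.

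The cost is a few sentences in Section 9.2 and reprogrammed eligibility flags; no new data are needed. Under route 1, patients whose assigned date falls after April 30, 2018 are lost. Under route 2, some treated patients are lost if the prior-record rule applies to all. Any 12-month look-back before the first IPF code is incomplete for patients first coded before October 2014, because data start on October 1, 2013. A window ending at the first IPF code also misses later other-ILD codes in every cohort, including those the present rule is worded to catch.

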9.3 VARIABLES

9.3.1 Exposures

Both nintedanib (Ofev, BI) and pirfenidone (Esbriet, Genentech) were approved by the US FDA on October 15, 2014 (reflected by start of selection window in this study). Nintedanib initiators will be identified using prescription records for nintedanib, with the index date being the first prescription in the EMR during the selection window. Similarly, pirfenidone initiators will be identified using prescription records for pirfenidone; index date is first prescription. New users of these medications will be selected into the study, excluding those who initiated both medications on index. The number of patients who initiated both medications on index will be reported during the patient attrition. Since the purpose of this study is to identify predictors of IPF treatment initiation, no post-index follow-up measures will be reported. Patients who switched between the treatments during the pre-index period will be excluded because of the new user design, and those who switch after the index date will not be a concern as no study measures will be evaluated during the post-index period for the objectives of this study. No validation will be performed on the exposures of interest as exposure ascertainment relies on evidence of ≥ 1 prescription record.

9.3.2 Outcomes

9.3.2.1 Primary outcomes

The primary outcome will be the ASD and p-value comparing baseline patient characteristics (as described in section 9.3.3) between the following cohorts:

- Nintedanib vs. pirfenidone
- Nintedanib vs. untreated
- Pirfenidone vs. untreated

9.3.2.2 Secondary outcomes

The secondary outcomes will be the probabilities (propensity scores) of receiving one treatment over another (or probability of receiving antifibrotic treatment) between the following cohorts:

- Nintedanib vs. pirfenidone
- Treated patients (i.e., nintedanib or pirfenidone) vs. untreated

9.3.2.3 Further outcomes

None.

9.3.3 Covariates

The following measures will be evaluated during the 12-month baseline period, including index date, unless otherwise noted. Measures will be reported separately for each of the three cohorts.

For nintedanib and pirfenidone cohorts only:

- Index medication (n, %)
 - Nintedanib
 - Pirfenidone
- Average daily dose of the index prescription
 - Nintedanib (mean, SD, median, min, max) and categories (n, %)
 - 100 mg
 - 150 mg
 - Unknown
 - Pirfenidone (mean, SD, median, min, max) and categories (n, %)
 - 267 mg
 - Unknown
- Time from the earliest diagnosis for IPF to index (mean, SD, median, min, max)
- Prescribing physician specialty (n, %)
 - Primary care
 - Internal medicine
 - Pulmonologist
 - Other

For all cohorts:

Demographic characteristics

- Age (mean, SD, median, min, max) and age categories on index date (n, %)
 - 40-49
 - 50-59

- 60-69
 - ≥ 70
- Gender (n, %)
 - Male
 - Female
- Index year (n, %)
 - 2014
 - 2015
 - 2016
 - 2017
 - 2018
- Region (n, %)
 - Northeast
 - Midwest
 - South
 - West
- Race/ethnicity (n, %) (expected to be missing for about 40% of patients)
 - White
 - African American
 - Hispanic
 - Asian
 - Other
 - Unknown
- Payer type (n, %)
 - Commercial
 - Medicaid
 - Medicare
 - Self-Insured
 - Other/Unknown

Clinical characteristics (based on ICD-9/10-CM procedure and diagnosis codes, laboratory test codes, CPT codes and NDC/RxNorm (to be included in Appendix), as well as other information in the EMR encounter files)

- Body weight (lbs; mean, SD, median, min, max)
 - Body mass index (BMI; kg/m²; mean, SD, median, min, max)
 - BMI category, defined using BMI field (n, %)
 - Underweight ($<18.5 \text{ kg/m}^2$)
 - Normal weight (18.5 to 24.99 kg/m²)
 - Overweight (25 to 29.99 kg/m²)
 - Obese (30 to 34.99 kg/m²)
 - Very obese ($\geq 35 \text{ kg/m}^2$)

- Blood pressure (BP)¹⁴ (n, %)
 - Diastolic BP
 - Normal (<80 mmHg)
 - High (≥ 80 mmHg)
 - Systolic BP
 - Normal (<120 mmHg)
 - Elevated (≥ 120 and < 129 mmHg)
 - High (≥ 130 mmHg), further broken down as follows if data allow
 - Stage 1 (≥ 130 and < 139 mmHg)
 - Stage 2 (≥ 140 mmHg)
- Smoking status at index (n, %); excluding smokeless tobacco; categories to be finalized during analysis
 - Smoker
 - Non-smoker, further broken down as follows if data allow
 - Previous smoker
 - Never smoker
 - Unknown/missing
- Alcohol consumption (n, %)
 - Yes
 - No
 - Unknown/missing
- Charlson comorbidity index (CCI)¹⁵ (mean, SD, median, min, max) and categories (n, %), defined using ICD diagnosis codes
 - 0
 - 1
 - 2
 - 3
 - 4+
- Respiratory comorbidities¹⁶ (n, %), defined using ICD diagnosis codes
 - COPD (Chronic obstructive pulmonary disease), includes chronic bronchitis and emphysema
 - Pulmonary hypertension
 - Obstructive sleep apnea
 - Lung cancer
 - Pulmonary embolism
 - Asthma
 - Acute respiratory distress syndrome
 - Pulmonary edema
 - Cough
 - Upper respiratory tract infection (includes acute bronchitis)
 - Bronchitis (not specified as acute or chronic)

- Sinusitis
- Gastroesophageal reflux disease (GERD) (n, %), defined using ICD diagnosis codes
- Metabolic disorders¹⁶ (n, %), defined using ICD diagnosis codes
 - Obesity (defined as ICD-9 code 278.0 or ICD-10 code E66 or BMI ≥ 30 kg/m²)
 - Diabetes
 - Any diabetes
 - Type 1 diabetes
 - Type 2 diabetes¹⁶
 - Dyslipidemia (includes hypercholesterolemia and hyperlipidemia)
- Cardiovascular disorders¹⁶ (n, %), defined using ICD diagnosis codes
 - Arrhythmia
 - Atrial fibrillation
 - Heart failure
 - Ischemic heart disease
 - Stroke
 - Hypertension (includes systemic arterial hypertension)
 - Peripheral arterial diseases
 - Cardiomyopathy
- Mental disorders (n, %), defined using ICD diagnosis codes
 - Depression
 - Anxiety
 - Schizophrenia
 - Dementia
 - Bipolar disorders
- Renal impairment (n, %), defined using ICD diagnosis codes
- Hepatic impairment (n, %), defined using ICD diagnosis codes
- Laboratory measures (to the extent that the data allow; tests will be identified by procedure codes and EMR data fields; if repeated measurements of a test are observed, the one closest to the index date will be reported, with the exception of several renal and liver measures (where noted) when any evidence of patient history of the condition during baseline will take precedent over the measure closest to index)
 - Anticoagulation tests (n, %)
 - Prothrombin time (n, %)
 - High (>14 seconds)
 - Normal (10-14 seconds)
 - Low (<10 seconds)
 - Activated partial thromboplastin time (aPTT; n, %)
 - Normal (30-40 seconds)
 - Elevated (41-70 seconds)

- Critical (>70 seconds)
- Bleeding time (n, %)
 - Normal (1-9 minutes)
 - Platelet dysfunction (10-15 minutes)
 - Critical (>15 minutes)
- Hematologic markers
 - Blood hemoglobin (mean, SD, median, min, max)
 - Blood hematocrit (mean, SD, median, min, max)
 - Red blood cell count (mean, SD, median, min, max)
 - Platelet count (n, %)
 - Low (<150,000 platelets/mcL)
 - Normal (150,000-450,000 platelets/mcL)
 - High (>450,000 platelets/mcL)
 - Conventional C - reactive protein (n, %)
 - Normal (≤ 5.0 mg/L)
 - High (>5.0 mg/L)
- Liver function tests (n, %)
 - Alanine transaminase (ALT; n, %); patient history of high ALT level suggesting hepatic impairment will be reported and take precedent to ALT value closest to index
 - Low (<7 U/L)
 - Normal (7 – 56 U/L)
 - High (>56 U/L)
 - Aspartate transaminase (AST; n, %); patient history of high AST level suggesting hepatic impairment will be reported and take precedent to AST value closest to index
 - Low (<5 U/L)
 - Normal (5 – 40 U/L)
 - High (>40 U/L)
 - Alkaline phosphatase (ALP; n, %)
 - Low (<44 IU/L)
 - Normal (44 – 147 IU/L)
 - High (>147 IU/L)
 - Gamma-glutamyl transpeptidase (GGT; n, %)
 - Low (<9 U/L)
 - Normal (9-48 U/L)
 - High (>48 U/L)
 - Total bilirubin (n, %); patient history of high bilirubin level suggesting hepatic impairment will be reported and take precedent to value closest to index
 - Low (<0.2 mg/dL)

- Normal (0.2-1.2 mg/dL)
 - High (>1.2 mg/dL)
 - Kidney function tests (n, %)
 - Albumin to creatinine ratio (ACR; n, %)
 - Normal (<30)
 - Microalbuminuria (30-300)
 - Macroalbuminuria (>300)
 - Glomerular filtration rate (GFR; n, %); patient history of low GFR suggesting renal impairment will be reported and take precedent to value closest to index
 - Low (<90 mL/min/1.73m²)
 - Normal (90 – 120 mL/min/1.73m²)
 - High (>120 mL/min/1.73m²)
 - Serum creatinine (mean, SD, median, min, max); patient history of high serum creatinine level suggesting renal impairment will be reported and take precedent to value closest to index
 - Cholesterol levels (n, %)
 - Total cholesterol (mg/dL; n, %)
 - Normal (<200 mg/dL)
 - Borderline high (200-239 mg/dL)
 - High (\geq 240 mg/dL)
 - Triglyceride (mg/dL; n, %)
 - Normal (<150 mg/dL)
 - Borderline high (150-199 mg/dL)
 - High (\geq 200 mg/dL)
 - Cholesterol in high-density lipoprotein (HDL; n, %)
 - Normal (\geq 40 mg/dL)
 - Abnormal (<40 mg/dL)
 - Cholesterol in low-density lipoprotein (LDL; n, %)
 - Normal (<100 mg/dL)
 - Borderline high (100 – 159 mg/dL)
 - High (\geq 160 mg/dL)
- Pulmonary function tests (PFTs) indicative of IPF severity (n, %)
 - FVC (n, %)
 - Normal (\geq 80%)
 - Abnormal (<80%)
 - Forced expiratory volume in one second (FEV1) /FVC ratio (n, %)
 - Normal (\geq 70%)
 - Abnormal (<70%)
 - Total lung capacity (TLC) (mean, SD, median, min, max)
 - Carbon monoxide diffusing capacity of the lung (DLCO; n, %)

- Normal (>75% of predicted)
- Mild to moderate decrease (40-74% of predicted)
- Severe decrease (<40% of predicted)
- Oxygen saturation (n, %)
 - Normal (95-100%)
 - Below normal (<95%)
- GAP index¹⁸ (n, %), if data allow
 - Calculated using information on age, gender and FVC
 - Stage I (0-3 points)
 - Stage II (4-5 points)
 - Stage III (6-8 points)

Treatment history during the pre-index period (not including index date):

- Pharmacological interventions (n, %)
 - Other treatments (as per ATS/ERS/JRS/ALAT guidelines¹⁹)
 - Selective tyrosine kinase inhibitor against platelet derived growth factor (Imatinib)
 - Prednisone
 - Azathioprine
 - N-acetylcysteine
 - Selective endothelin receptor antagonist (ambrisentan)
 - Phosphodiesterase-5 inhibitor (sildenafil)
 - Dual endothelin receptor antagonists (macitentan, bosentan)
 - Corticosteroids
 - Inhaled corticosteroids
 - Oral corticosteroids
 - Bronchodilators
 - SABA
 - LABA
 - Anticholinergics
 - Other beta agonists
 - GERD therapy
 - H-2 receptor blockers
 - Proton pump inhibitors
 - Antacids
 - Cardiovascular drugs
 - Antianginals
 - Antihypertensives
 - Antiarrhythmics
 - Antiplatelets
 - Anticoagulants

- Antidiabetes drugs
- Anti-infectives
- Anticonvulsants
- Anti-anxiety drugs
- Antidepressants
- Antipsychotics
- Antihyperlipidemics
- Non-pharmacological interventions (n, %)
 - Surgical procedures (n, %)
 - Lung transplantation
 - Esophageal sphincter reinforcement
 - Lung cancer surgeries
 - Supportive therapy (n, %)
 - Oxygen therapy
 - Pulmonary rehabilitation
 - Diagnostic procedures (n, %)
 - High resolution computed tomography (HRCT)
 - Surgical lung biopsy
 - Chest X-rays
 - 6-minute walk test/pulmonary stress test
 - Spirometry
 - Bronchoalveolar lavage

Treatment on the index date (pharmacological interventions only):

- For each of the following treatments, the number and proportion of patients with and without the treatment on the index date will be reported (days' supply to be considered when exploring treatment use on index)
 - Other treatments (as per ATS/ERS/JRS/ALAT guidelines¹⁹; n, %)
 - Selective tyrosine kinase inhibitor against platelet derived growth factor (Imatinib)
 - Prednisone
 - Azathioprine
 - N-acetylcysteine
 - Selective endothelin receptor antagonist (ambrisentan)
 - Phosphodiesterase-5 inhibitor (sildenafil)
 - Dual endothelin receptor antagonists (macitentan, bosentan)
 - Corticosteroids (n, %)
 - Inhaled corticosteroids
 - Oral corticosteroids
 - Bronchodilators (n, %)
 - SABA

- LABA
- Anticholinergics
- Other beta agonists
- GERD therapy (n, %)
 - H-2 receptor blockers
 - Proton pump inhibitors
 - Antacids
- Cardiovascular drugs (n, %)
 - Antianginals
 - Antihypertensives
 - Antiarrhythmics
 - Antiplatelets
 - Anticoagulants
- Antidiabetes drugs (n, %)
- Anti-infectives (n, %)
- Anticonvulsants (n, %)
- Anti-anxiety drugs (n, %)
- Antidepressants (n, %)
- Antipsychotics (n, %)
- Antihyperlipidemics (n, %)

[figure not shown]
